9.5.2 Analyses of Secondary Efficacy Endpoint(s)

Analysis of the secondary endpoints (including percent change from baseline at week 36 in ApoB and LDL-C, and percent change from baseline at week 48 in ApoB, Lp(a) and LDL-C) will be performed similarly to the analysis of the primary endpoint. There will be no multiplicity adjustment for the secondary efficacy endpoints.

9.5.3 Analyses of Exploratory Efficacy Endpoint(s)

Exploratory endpoints of percent change from baseline at scheduled visits in Lp(a), LDL-C and ApoB will be analyzed using repeated measures linear effects model including terms for treatment group, stratification factors, scheduled visit and the interaction of treatment group with scheduled visit will be used; and achievements of Lp(a) at scheduled visits (including achievement of Lp(a) < 125nmol/L) will be analyzed using CMH test as specified in Table 2. Subject incidence of positively adjudicated events (overall and by event type as defined in protocol) and change from baseline in PROMIS Global Health measures at scheduled visits will be summarized by treatment group using descriptive statistics.

Descriptive summary for non-HDL-C, HDL-C, VLDL-C and Triglycerides will be provided by scheduled visits.

9.6 Safety Analyses

9.6.1 Adverse Events

The Medical Dictionary for Regulatory Activities (MedDRA) version 24.0 or later will be used to code all events categorized as adverse events to a system organ class and a preferred term. All adverse event tables will be summarized by actual treatment group. All adverse event summaries will include all treatment-emergent events reported on the Event eCRF, including CEC reviewed events.

The subject incidence of adverse events will be summarized for all treatment-emergent adverse events, serious adverse events, adverse events leading to withdrawal of investigational product, and fatal adverse events.

Subject incidence of all treatment-emergent adverse events will be provided by preferred term in descending order of frequency. Treatment-emergent adverse events and treatment-emergent serious adverse events will be tabulated by system organ class, high level term, and preferred term in descending order of frequency. Treatment-emergent adverse events leading to discontinuation of investigational product, treatment-emergent fatal adverse events, treatment-related treatment-emergent adverse events, and treatment-related treatment-emergent serious adverse events will be provided by system organ class, and preferred term in descending order of frequency.

Subject incidence of adverse events of interest (peripheral neuropathy, myopathy, hypersensitivity reactions, effects on renal and liver function, hyperglycemia (including new onset diabetes), thrombocytopenia, coagulation parameters, immune-inflammatory and injection site reactions) will be summarized by category and preferred term.

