2.3 Benefit/Risk Assessment

Elevated plasma Lp(a) has been identified as a strong independent risk factor for the development and progression of atherosclerotic disease (Ellis et al, 2017). Lp(a) has been associated with increased risk for myocardial infarction, aortic valve stenosis development, carotid artery stenosis and abdominal aorta aneurism progression. High plasma Lp(a) concentration is genetically defined, cannot be controlled by healthy habit modifications and is not effectively controlled by any of the currently available lipid-reducing medications. Therefore, the development of a novel agent to lower high Lp(a) concentrations is a valid approach to confer additional protection against cardiovascular disease. Although definitive evidence that the reduction in plasma Lp(a) will provide cardiovascular risk reduction is not yet available, mendelian randomization epidemiologic studies, plasma apheresis cohort results, and experimental data suggest a causal role for elevated Lp(a) (Averna et al, 2017; Nordestgaard and Langsted, 2016; Ohro-Melander, 2015) and provide the rationale for exploring the therapeutic concept.

There are no identified risks for olpasiran and potential risks are limited to liver enzyme elevation and hypersensitivity reactions. Other events of interest for olpasiran, that have not been borne out either by the non-clinical or available clinical data, but that are based

on the siRNA/oligotherapeutics platform include: effects on platelets and coagulation, immune inflammatory response, and peripheral neuropathy. Additionally, very low levels of Lp(a) have been associated with increased incidence of type 2 diabetes, but whether pharmacologic lowering of Lp(a) would be associated with an increased risk for development of type 2 diabetes is unknown (Paige et al, 2017; Ye et al, 2014). These risks have not been borne out by either the non-clinical data or clinical data to date for olpasiran.

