5.2 Exclusion Criteria

Subjects are excluded from the study if any of the following criteria apply:

Disease Related

- 201 Severe renal dysfunction, defined as an estimated glomerular filtration rate (eGFR) < 30 mL/min/1.73 m² during screening
- 202 History or clinical evidence of active liver disease or hepatic dysfunction, defined as aspartate aminotransferase (AST) or alanine aminotransferase (ALT) > 3 x upper limit of normal (ULN), or total bilirubin (TBL) > 2 x ULN during screening
- 203 Inherited or other bleeding disorders
- 204 Recent major cardiovascular event (myocardial infarction, unstable angina, PCI, CABG, or stroke) within 6 months prior to day 1
- 205 Planned cardiac surgery, PCI or carotid stenting, or planned major non-cardiac surgery during the study period

Other Medical Conditions

- 206 Malignancy (except non-melanoma skin cancers, cervical in-situ carcinoma, breast ductal carcinoma in situ, or stage 1 prostate carcinoma) within the last 5 years prior to day 1
- 207 Moderate to severe heart failure (New York Heart Association (NYHA) Functional Classification III or IV at day 1) or last known left ventricular ejection fraction $< 30\%$
- 208 Uncontrolled cardiac arrhythmia defined as recurrent and highly symptomatic ventricular tachycardia, atrial fibrillation with rapid ventricular response, or supraventricular tachycardia that are not controlled by medications, in the past 3 months prior to day 1
- 209 Uncontrolled hypertension at day 1, defined as an average systolic blood pressure of ≥ 160 mmHg or an average diastolic blood pressure of ≥ 100 mmHg at rest
- 210 Fasting triglycerides ≥ 400 mg/dL (4.5 mmol/L) during screening

- 211 Type 1 diabetes or poorly controlled ($\text{HbA1c} \geq 8.5\%$) type 2 diabetes mellitus as determined by central laboratory at screening
- 212 Known active infection or major hematologic, renal, metabolic, gastrointestinal or endocrine dysfunction, or a chronic disease or infection (eg, HIV) that is not currently stable and appropriately managed in the judgment of the investigator at day 1

Prior/Concomitant Therapy

- 213 Previously received treatment with antisense oligonucleotides (ASO), siRNA therapies (eg, inclisiran), or any experimental therapy targeting Lp(a)
- 215 Currently undergoing lipid apheresis or < 3 months since last apheresis treatment at day 1

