6.7.2 Concomitant Treatment

Throughout the study, investigators may prescribe any concomitant medications or treatments deemed necessary to provide adequate supportive care except for those listed in Section 6.1.6.

Any lipid-altering therapy, including statins, that were being taken by the subject at screening and enrollment must remain stable throughout the study, including the screening, treatment and extended safety follow-up periods. Lipid-altering therapies are not required for study participation. If any changes to lipid-altering therapies are medically warranted after randomization, the Amgen medical monitor or designee should be consulted before making the change, if possible.

Concomitant therapies are to be collected from informed consent through the **EOS**. For lipid-altering therapies and diabetes therapies (if applicable), collect therapy name, dose, unit, frequency, start and stop dates, reason for stop or change. For all other concomitant therapies, collect therapy name, start and stop dates.

7. Discontinuation Criteria

Subjects have the right to withdraw from investigational product and/or other protocol-required therapies, protocol procedures, or the study as a whole at any time and for any reason without prejudice to their future medical care by the physician or at the institution.

The investigator and/or sponsor can decide to withdraw a subject(s) from investigational product, device, and/or other protocol-required therapies, protocol procedures, or the study as a whole at any time prior to study completion for the reasons listed in Sections [7.1](#), [7.2.1](#), and [7.2.2](#).

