8.2.5 Clinical Laboratory Assessments

Refer to Section 11.2 for the list of clinical laboratory tests to be performed and to the Schedule of Activities (Table 1-1) for the timing and frequency.

The investigator is responsible for reviewing laboratory test results and recording any clinically relevant changes occurring during the study in the Events CRF. The investigator must determine whether an abnormal value in an individual study subject represents a clinically significant change from the subject's baseline values. In general, abnormal laboratory findings without clinical significance (based on the investigator's judgment) are not to be recorded as adverse events. However, laboratory value changes that require treatment or adjustment in current therapy are considered adverse events. Where applicable, clinical sequelae (not the laboratory abnormality) are to be recorded as the adverse event.

All protocol-required laboratory assessments, as defined in Section 11.2, must be conducted in accordance with the laboratory manual and the Schedule of Activities (Table 1-1).

Laboratory/analyte results that could unblind the study will not be reported to investigative sites or other blinded personnel until the study has been formally unblinded. In order to protect the blinding of the double-blind treatment period, the following labs will be blinded to the Amgen study team and site staff after day 1 until the study has been formally unblinded, and will not be reported to sites:

- Serum Lp(a)
- Lipid panel (see Appendix 2 Section 11.2 for a list of analytes)
- high sensitivity C-reactive protein (hs-CRP)
- **high sensitivity Interleukin 6 (hs-IL-6)**
- anti-olpasiran antibodies
- ApoA1
- ApoB

In addition, investigators and staff involved with this trial and all medical staff involved in the subject's medical care should not perform non-protocol testing of these analytes during a subject's study participation and until the end of the study, to prevent unblinding the patient and site to the treatment assignment, except when it is medically necessary. If a local lipid panel is drawn, all reasonable steps must be undertaken to avoid informing the subject and study personnel of the results.

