9.1 General Considerations

Unless specified otherwise, efficacy analyses will be performed on the FAS by randomized treatment group, and safety analyses will be performed on the FAS by actual treatment group.

For the Primary Analysis (as described in Section 7.2), all data up to the primary analysis data cut-off date will be included. Based on the snapshot for the primary analysis, efficacy and safety analyses will be performed. Testing will be performed for endpoints defined up to week 36. Descriptive summary will be provided for all available visits by period (ie. Treatment period and extended safety follow-up period).

For the End of Treatment Period Analysis (as described in Section 7.3), all data up to the end of treatment period analysis cut-off date will be included. Testing will be performed for endpoints defined up to week 48. Descriptive summary will be provided for all available visits by period (ie. Treatment period and extended safety follow-up period).

For the Final analysis (as described in Section 7.4), all efficacy and safety analyses during the extended follow-up period will be performed based on the snapshot for the final analysis.

Subject disposition, demographics, baseline characteristics, and exposure to IP will be summarized.

All categorical variables will be summarized using the number and percent of subjects and all continuous variables will be summarized using mean, standard error or standard deviation, median, minimum, maximum, and number of subjects with observations.

Multiplicity Adjustment Method:

The Hochberg procedure will be used to control the type I error for multiple comparisons between active and placebo groups in the primary endpoint. The primary endpoint includes percent change in Lp(a) from baseline at week 36 for olpasiran SC Q12W groups and placebo. Percent change in Lp(a) from baseline for Q24W group is defined as exploratory endpoint.

A summary of the analyses for each planned analysis can be found in Table 2.

Table 2. Summary of Analyses

Analyses	Primary Analysis (all data up to primary analysis data cut-off date)	End of Treatment Period Analysis (all data up to End of Treatment Period Analysis data cut-off date)	Final Analysis (all data based on final snapshot)

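### New-onset diabetes is reported only as adverse events in a hyperglycemia category over the whole FAS; a count among subjects without baseline diabetes, using the HbA1c, glucose and therapy data already collected, should be added

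*SAP*

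**What the plan says.** **The question.** Protocol 2.3 notes that "very low levels of Lp(a) have been associated with increased incidence of type 2 diabetes" and says it is unknown whether pharmacologic lowering has the same association. It adds that this and the other listed risks have not been borne out by the olpasiran data so far.

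**The planned measure.** SAP 9.6.1 lists adverse events of interest, among them "hyperglycemia (including new onset diabetes), thrombocytopenia, coagulation parameters, immune-inflammatory and injection site reactions) will be summarized by category and preferred term". On the source of events it says: "All adverse event summaries will include all treatment-emergent events reported on the Event eCRF, including CEC reviewed events". On the population, SAP 9.1 says that "safety analyses will be performed on the FAS by actual treatment group".

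**Who is enrolled.** Exclusion criterion 211 (Protocol 5.2) removes type 1 diabetes and poorly controlled (HbA1c of 8.5% or more) "type 2 diabetes mellitus as determined by central laboratory at screening". Type 2 diabetes below that limit may enter.

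**When a laboratory change becomes an event.** Protocol 8.2.5 says that, in general, "abnormal laboratory findings without clinical significance (based on the investigator's judgment) are not to be recorded as adverse events". It then says that changes requiring treatment, or an adjustment of treatment, are adverse events.

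**What is collected.** HbA1c and fasting glucose are in the Schedule of Activities, and SAP Appendix A gives glucose and HbA1c analysis windows at weeks 4, 12, 24, 36, 48 and 72. Protocol 8.2.1.3 collects diabetes history. Protocol 6.7.2 says: "For lipid-altering therapies and diabetes therapies (if applicable), collect therapy name, dose, unit, frequency, start and stop dates".

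**Laboratory analyses.** SAP 9.6.2 plans descriptive statistics for selected parameters and CTCAE shift tables for analytes of interest, naming neither HbA1c nor glucose. It sets threshold categories only for creatine kinase and liver tests.

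**The concern.** The sponsor named the question and listed new-onset diabetes as an event of interest, so a figure will be reported. Three features make that figure hard to read.

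- **Denominator.** Subjects who already have diabetes are counted as if they could develop it.
- **Category.** A glucose rise in a subject with known diabetes and a new diagnosis add to the same category total.
- **Source.** A subject whose HbA1c or glucose rises into the diabetic range, without treatment and without the investigator judging it clinically significant, need not appear at all. No planned laboratory analysis counts such subjects.

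At stake is the new-onset incidence per arm that the sponsor takes into phase 3 planning. It would be lower than the incidence among subjects at risk by an amount the planned table does not show, although the data for a direct count are already in the database.

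**Working it through.** **Inputs from the documents.** 58 subjects per arm (Protocol 4.2), so 4 × 58 = 232 active. At least 48 per arm, 192 active, 5% drop-out and an incidence of 1/60 (SAP 3.2).

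**Inputs assumed, because the documents give none.**
- d, the share with diabetes at baseline: 20% to 40%
- q, the share of known diabetics with a hyperglycemia event, equal in both groups: 5% to 15%
- new-onset incidence among those at risk: 3% on placebo, 6% on active

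**1. The plan's own safety figure.** SAP 3.2 claims 95% confidence of seeing one case of an event with incidence 1/60. With n = 192 × 0.95 ≈ 182, 1 − (59/60)^182 = 95.3%. The figure reproduces, but it treats every subject as at risk.

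**2. The same figure for new-onset diabetes.** The number at risk is 182 × (1−d).

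| d | At risk | Chance of ≥1 case at 1/60 | A true 1/60 shown over the FAS |
|---|---|---|---|
| 20% | 146 | 91.4% | 1/75 |
| 30% | 127 | 88.2% | 1/86 |
| 40% | 109 | 84.0% | 1/100 |

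The third column reflects trial size, and no change of denominator restores it.

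**3. Effect of the denominator on incidence.** FAS incidence = (1−d) × at-risk incidence. For an arm of 58 with 2 cases:
- over the FAS: 2/58 = 3.4%
- among those at risk, d = 20%: 2/46.4 = 4.3%
- among those at risk, d = 40%: 2/34.8 = 5.7%

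This applies to new-onset cases. The category total also contains events in known diabetics, so it can lie above or below the at-risk incidence.

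**4. Effect of the denominator on the ratio.** With the same expected d in every randomised arm, (1−d) cancels: [(1−d) × 6%] / [(1−d) × 3%] = 2.0.

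**5. Effect of the mixed category on the ratio.** Category incidence = (1−d) × new-onset incidence + d × q.
- d = 20%, q = 5%: placebo 0.024 + 0.010 = 3.4%; active 0.048 + 0.010 = 5.8%; ratio 1.71.
- d = 40%, q = 15%: placebo 0.018 + 0.060 = 7.8%; active 0.036 + 0.060 = 9.6%; ratio 1.23.

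A true ratio of 2.0 therefore reads as 1.71 to 1.23 in the category total.

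**6. Missed cases.** The documents give no rate. Purely as illustration, if adverse event reporting caught half of cases, 1 − (1 − 1/120)^n gives 70.5% (n = 146) to 59.8% (n = 109).

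**7. Power after the fix.** After 5% drop-out there are about 55 placebo and 220 active subjects. At d = 20%, 44 and 176 are at risk.
- Pooled proportion: (44 × 0.03 + 176 × 0.06)/220 = 0.054.
- Null standard error: √[0.054 × 0.946 × (1/44 + 1/176)] = 0.0381.
- Alternative standard error: √[0.03 × 0.97/44 + 0.06 × 0.94/176] = 0.0313.
- Power at two-sided 5%: Φ[(0.03 − 1.96 × 0.0381)/0.0313] = 7.7%.

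At d = 40% it is 6.0%. These are rough normal approximations with few expected cases. Using the alternative standard error throughout gives Φ(0.03/0.0313 − 1.96) ≈ 16% at d = 20%, which is still low. Keeping the FAS denominator gives 7.6% and 5.8% by the pooled method, so the denominator hardly changes power.

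**The case against.** The strongest reply is that the plan already covers most of this.

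- **Reporting.** Protocol Appendix 4 makes a condition newly detected or diagnosed after dosing an adverse event, and Protocol 8.2.5 does the same for laboratory changes needing treatment. HbA1c and glucose are not on the list of blinded analytes, so sites can see them. This stands. A reader might infer that the reported incidence is shown to be too low because cases are missed. The documents do not show that; the gap is the untreated conversion judged not clinically significant, and its size is unknown.
- **Separate rows.** Events of interest are summarised by preferred term as well as by category. This stands in part: diabetes terms get their own rows, but a row does not show which subjects had diabetes at baseline.
- **Laboratory summaries.** Protocol 9.4.2.3.2 plans by-visit statistics and grade shifts, and the Appendix A windows suggest that HbA1c and glucose will be summarised. So the laboratory data are not ignored. But SAP 9.6.2 does not name these analytes, and means and shift tables do not count new cases.
- **Randomisation.** A reader might infer that the whole-FAS denominator biases the comparison of arms. It does not (step 4).
- **Dose.** A reader might also take the diabetes question to be dose-dependent. The documents link dose to Lp(a) suppression, not to diabetes.
- **Safety review.** Protocol Appendix 3 has an unblinded internal team comparing event rates and reviewing relevant laboratory results. That protects subjects during the trial but does not define what is reported.

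**Conclusion.** The point holds in a limited form. Followed as written, SAP 9.6.1 gives a new-onset diabetes incidence over a denominator that includes subjects who cannot become cases. It is understated by the factor (1−d): by 20% to 40% if d is 20% to 40%, which is an assumption. The between-arm ratio is unaffected by the denominator. The mixed category total can attenuate it, from 2.0 to between 1.71 and 1.23 under the assumed inputs, and the preferred-term rows limit that in part. Under-ascertainment is a reasoned possibility confined to untreated conversions, with no figure to size it.

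It would go too far to say that the fix makes an absence of signal informative for phase 3. Power for an assumed 3% versus 6% stays around 6% to 8% by the pooled approximation. The gain is a correctly defined incidence and a more complete case count. That is worth having because the sponsor raised the question and already collects the data.

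**What to change.** In SAP 9.6.1 and 9.6.2, add a descriptive new-onset diabetes outcome.

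- **Population.** FAS subjects without diabetes at baseline, judged by medical history, diabetes therapy, and baseline HbA1c and fasting glucose.
- **Case.** Any of: a diabetes adverse event; newly started diabetes therapy; or post-baseline HbA1c or fasting glucose at or above a cut-off that the sponsor prespecifies. The documents contain no such cut-off and none is proposed here.
- **Reporting.** n/N at risk with a confidence interval by actual treatment group. Report worsening of known diabetes separately, and summarise change in HbA1c by baseline diabetes status.

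The existing category and preferred-term tables can stay. The cost is SAP wording and one or two extra tables, with no new data collection. The reported incidence may be higher than under the present plan, and the between-group comparison should be labelled descriptive.

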9.6.2 Laboratory Test Results

Selected laboratory parameters will be summarized using descriptive statistics at scheduled visits. Laboratory shift tables using the CTCAE v5.0 or later grading will be used for analytes of interest, when applicable. The results will be based on the maximum (e.g., worst) shift from baseline to the EOS.

In addition, creatine kinase (CK) and liver function test (LFT) abnormalities will be assessed by the incidence overall and by visits of the following categories:

- CK > 5 x ULN
- CK > 10 x ULN
- ALT or AST > 3 x ULN
- ALT or AST > 5 x ULN

- Total bilirubin > 2 x ULN
- (ALT or AST > 3 x ULN) and Total bilirubin > 2 x ULN and Alkaline Phosphatase <2 x ULN

